- 2. This prospective study will assess the relative effects of two temperatures (in degrees Celsius) used to ablate the targeted nerves in regards to pain management and possible complications.

Research Question:

Which temperature used to produce RF lesion (80°C or 90°C) is associated with better overall improvement in facet-mediated chronic low back pain?

Specific Hypotheses:

Primary

Lumbar facets medial branches RFA at 90°C provides more overall pain relief (i.e. percent of improvement), when compared to ablation at 80°C with no additional adverse events.

Secondary

Ablation of the lumbar facets nerve supply at 90°C will provide better improvement in the functionality level, general mood and quality of life as measured by VAS (Visual Analog Scale) pain score, Pain Disability Index (PDI), McGill Pain and Beck Inventory (BI) questionnaire scores than those receiving the ablation at 80°C. Furthermore, it is associated with less opioid consumption, no additional unwanted adverse events and/or complications along with less need to repeat RFA procedure over one year follow-up period.

Significance/Importance:

Chronic lower back pain (LBP) is a significant health care issue in the United States and the world. Chronic LBP contributes to decreased quality of life, decreased functionality and increased utilization of health care resources. The causes of chronic LBP tend to be multi-factorial. Arthropathy of the lumbar facet joints is thought to be a common etiology (15-45%) (1). Radiofrequency Ablation (RFA) of the medial branch nerve of the facet joint is a well-established treatment modality used to decrease facet joint pains. However, a wide range

Protocol Version 3 Revision Date: 10/15/2019 of temperature is being used (70-90 degrees Celsius). In addition, the optimal temperature that provides the best patient outcomes with the least side effects is not well established in the pain management literature.

Summary of Literature:

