In a retrospective study done at our department, 100 patients (50.3%) received RFA at 80°C and 99 patients (49.8%) received RFA at 90°C. there were no clear cut advantage of either

temperature. However, the preliminary analysis did not control for potentially confounding baseline demographics and disease related characteristics. Thirty eight (38%), 9 (9%), 37 (37%) and 16 (16%) patients undergoing RFA at 80°C reported no improvement, minimal improvement (<25%), moderate improvement (25-75%), and marked improvement (>75%) in symptoms respectively. Among patients undergoing RFA at 90°C, these numbers were 19 (19%), 1 (1%), 44 (45%) and 34 (35%), respectively. The proportional odds logistic regression model for relief did not indicate a significant difference in relief scores between the two groups (likelihood ratio test p=0.033, using an adjusted significant difference criterion at 0.025). Due to the factors discussed and the inherent limitations of the retrospective studies, we plan to prospectively study the issue in a double-blinded randomized fashion.

Study Population:

• Patient Population:

Subjects with chronic low back pain (LBP) of lumbar facet joints origin fulfill the other below inclusion criteria and do not meet any of the exclusion criteria will be recruited from Cleveland Clinic Pain management outpatient clinic.

• Inclusion Criteria:

- a. Age >18 years-old.
- b. Subjects who are able to give informed consent and to understand and comply with study requirements.
- c. Predominantly axial low back pain \geq 3 months in duration with no radicular pain below the knee that failed to conservative therapy.
- d. Subjects who have chronic back pain attributed to lumbar facet joints arthropathy based on clinical evaluation (paraspinal tenderness and/or facet loading test in the absence of signs and symptoms suggestive of focal neurological deficits).
- e. No history of previous back surgery at the intended treatment levels.
- f. Adequate response to the diagnostic block(s), 1 or more, at the same levels of the intended block (defined as \geq 70% pain relief).
- g. Patients who will undergo RFA of 3-4 lumbar facet medial branches on one side only.

• Exclusion Criteria:

- a. Subjects who decline to provide written consent or follow-up.
- b. Subjects who have a history of adverse reactions to local anesthetic.
- c. Subjects who are pregnant.

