- d. Subjects with bleeding disorders or active anticoagulation that cannot be stopped for few days close to the time of the procedure.
- e. Subjects who have an active systemic or local infection.
- f. Presence of radicular pain extending below the knee.
- g. Patients who have other specific etiology of low back pain (e.g. significant spinal canal stenosis or grade 2 or 3 spondylolisthesis).
- h. Secondary gain (i.e., ongoing litigation, worker's compensation or other financial incentives).
- i. Psychopathology including uncontrolled depression, somatization or poor coping skills.
- j. Physical factors including non-sedentary lifestyle, e.g.; morbid obesity (BMI >35kg/m²).
- k. History of previous RFA at the same level(s) in the previous 6 months.

Subject Withdrawal:

Subjects may voluntarily withdraw from the study at any time. Reasons for withdrawal will be recorded on the appropriate case report form (CRF). Pertinent data from such patients (either before or after the withdrawal) will be included in analysis if available, unless the patient explicitly states that they do not want their data to be included.

Terminating Subject Participation:

A subject's participation in the study may be terminated if continued participation in the study is not in the subject's best interest, in the investigator's opinion.

Methods:

• Study design:

This will be a prospective, randomized double-blinded study.

• Randomization:

After Institutional Review Board (IRB) approval and written consent, eligible patients, consenting to participate in the study will be randomly assigned to one of the two study groups (80°C or 90°C) based on computer-generated allocations which will be done immediately before use.

• Blinding:

Patient, physician performing the procedure and physician or research fellow assessing the outcomes will be blinded to the group assignment.

• Study Protocol:

Patients must meet all inclusion and exclusion criteria to be eligible for the study. After eligibility is confirmed, the patients will receive complete information about the study both verbally and in writing. Informed consent must be obtained from the patients prior to randomization and study-specific procedures. Once all eligibility criteria are fulfilled (including informed consent), the patients will be randomized, and treatment allocation will be performed. Key baseline patients characteristics, as well as patient's eligibility criteria, will be collected on case report forms.

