• Technique related data:

- The temperature of the probe used (80°C or 90°C)
- Duration of application of the RF probe is 90 seconds twice using 10mm active tip probe.
- Sensory stimulation 0.5mAmp
- Needle size 20G
- The number of ablated nerves.
- Side/Laterality.

• Outcomes Data:

Outcomes will be measured at baseline and 1, 3, 6 and 12 months follow-up visits post-procedure.

Primary outcomes:

Overall pain relief (i.e. percent of improvement) at each visit mentioned above.

Secondary outcomes:

- Postoperative Pain Scores in the subsequent visits using VAS at each visit mentioned above.
- Pain Questionnaires:
 - Pain Disability Index (PDI).
 - McGill Pain Questionnaire.
 - Beck Inventory (BI)
- Number of repeats of procedure in the first year after index procedure.

• Consumption of oral opioids in mg oral morphine equivalents recorded at the baseline before the procedure and then in the follow-ups post-procedure (1, 3, 6 and 12months).

- This table summarizes the morphine equivalent doses for the most commonly used morphine derivatives (7).

Drug Name	Oral dose equivalent to 30mg oral morphine sulfate	IV dose equivalent to 30mg oral morphine sulfate			
Morphine sulfate	30 mg (1:1 ratio)	10 mg (1:3)			
Hydromorphone	7.5 mg (1:4 ratio)	1.5 mg (1:20)			
Meperidine	300 mg(10:1 ratio)	100 mg (3.33:1)			
Methadone	12mg(1:2.5 ratio)	10 mg (1:3)			
Oxycodone	15 mg(1:2 ratio)	N/A			
Hydrocodone	30 mg(1:1 ratio)	N/A			
Codeine	200 mg(6.66:1 ratio)	120 mg (4:1)			

- The following formula will be used for Fentanyl transdermal patch:

- \circ 25 µg/h is equivalent to 87.5 mg morphine/24h
- \circ 50 µg/h is equivalent to 175 mg morphine/24h
- \circ 75 µg/h is equivalent to 262.5 mg morphine/24h
- \circ 100 µg/h is equivalent to 350 mg morphine/24h

• Adverse Events:

- Persistent paresthesia (yes/no)
- Nerve injury (yes/no)
- Infection (yes/no)
- Bleeding (yes/no)

• Data Analysis:

Standard descriptive statistics will be used to compare the randomized groups on baseline variables. Any obviously imbalanced co-variables (say, with a standardized difference greater than 0.20 in absolute value) will be adjusted for in both primary and secondary analyses. Our primary analysis will be intent-to-treat.

Primary Hypothesis:

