correlation structure. A model-based Wald test for regression model coefficients will be used to evaluate whether or not RFA temperature affects mean pain reduction.

Opioid Consumption:

As preliminary retrospective study showed, postoperative opioid consumption is largely binary in nature for this patient's population, as over 60% of our patients did not take any opioids. Thus, postoperative opioid consumption within a year of the first RFA will be analyzed as a binary outcome, i.e., any versus none (however, dosage information among the subset of patients taking any opioids will be described using medians and quartiles for each group). Multivariable logistic regression will be used to estimate the adjusted relative risk for postoperative opioid use comparing patients undergoing RFA at 90°C to patients undergoing RFA at 80°C. A logistic model-based Wald test for regression coefficients will be used to test the hypothesis of the effect of temperature on the postoperative opioids use (i.e., whether or not the relative risk is different from a value of 1.0).

Number of repeat of RFA procedures

Need for repeated RFA procedure over one year period will be analyzed as a count variable using a proportional odds logistic regression model. If the number of repeats greater than 1 is very rare, we will use a binary outcome of any RFA procedure comparing two groups of patients.

Complications:

Incidence of each individual complication will be reported for each group, with confidence intervals. Possible adverse events (persistent paresthesia, nerve injury, bleeding and infection) will be summarized into a single composite binary outcome, i.e., any versus none. The risk of experiencing one or more adverse events will be compared between RFA at 90°C and RFA at 80°C groups using logistic regression.

Type I error will be controlled at 5% for the secondary outcomes using the Bonferroni correction for simultaneous hypotheses. SAS 9.3 software (SAS Institute, Cary, NC) and R statistical software version 2.7.2 (The R Foundation for Statistical Computing, Vienna, Austria) will be used for all analyses and graphics.

Sample size considerations:

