Sample size estimation is based on the frequency distribution estimated across four categories of pain relief used in our preliminary retrospective study. Thus, for these calculations 38%, 9%, 37%, and 16% of patients undergoing RFA at 80°C are assumed to develop no improvement (=0%), minimal improvement (<25%), moderate improvement (25-75%), and marked improvement (>75%) in symptoms, respectively. We further assumed that the data was uniformly distributed across each category through simulation, and performed power calculations on the simulated data using categories of percent pain relief of 0, 1-10, 11-20, 21-30, \dots , 91 – 100. In order to have 90% power at the 0.0125 significance level at each time point (0.05/4 = 0.0125 at each time point) to detect a clinically significant shift in improvement of absolute 15% between RFA at 90°C and RFA at 80°C, a maximum of N=216 total patients would be required. Below we list the proportion of patients in each percent pain relief category as assumed for the sample size calculations described above. Although a 20% increase is in general what would be considered a clinically important improvement in pain relief, we plan for 15% since there may be a nontrivial fraction of patients who experience no relief in either group. Adjusting for 3 interim analyses and a final analysis would require a maximum of N=237. With the above parameters, there will be a cumulative 8%, 37%, 75%, and 100% chance of crossing a boundary at the 1st through 4th analyses if the alternative hypothesis is true as stated above.

Group	0	1-10	11-20	21-30	31-40	41-50	51-60	61-70	71-80	81-90	91-100
Control	.38	.041	.035	.06	.07	.067	.069	.087	.062	.057	.072
Experimental	0	0	.399	.041	.03	.083	.068	.064	.077	.078	.16

We plan to re-estimate sample size after obtaining at least 1 and 3 month continuous pain relief outcome for the first 60 patients, using the observed shape of the distribution and the variability of the outcome, but still based on an absolute 15 percent upward shift from the 80 degrees group. Type I error will be controlled using the methods in Kieser 2000 (9).

We will provide results to the Data and Safety Committee on efficacy and safety assessments, including conditional power analyses, but the committee will have final say on whether the study would progress to the next interim analysis or be stopped.

References

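### Repeat RFA (secondary endpoint): the one-year logistic analysis takes no account of incomplete follow-up, and a repeat is not tied to the treated side and levels

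*Combined protocol and SAP*

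**What the plan says.** The Secondary hypothesis expects the 90°C arm to show "less need to repeat RFA procedure over one year follow-up period". Outcomes Data lists the endpoint as "Number of repeats of procedure in the first year after index procedure" and sets the schedule: "Outcomes will be measured at baseline and 1, 3, 6 and 12 months follow-up visits post-procedure".

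Data Analysis, under the heading on the number of repeat procedures, states: "Need for repeated RFA procedure over one year period will be analyzed as a count variable using a proportional odds logistic regression model". If more than one repeat proves very rare, "we will use a binary outcome of any RFA procedure comparing two groups of patients". No offset, censoring, time-to-event method or missing-data rule is given for this endpoint.

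Subject Withdrawal allows patients to leave at any time. It says of their pertinent data ("either before or after the withdrawal) will be included in analysis if available", unless the patient refuses.

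On the treated site, inclusion criterion g reads: "Patients who will undergo RFA of 3-4 lumbar facet medial branches on one side only". Exclusion criterion k limits earlier RFA to the same level or levels. Technique related data lists the number of ablated nerves and the side, but not the levels. No date, side or level is listed for a later RFA.

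**The concern.** There are two gaps, and each can change what the comparison measures.

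- **Follow-up.** A proportional odds or binary logistic model of a one-year outcome treats each patient's count as complete. A patient seen to month 3 without a repeat must be scored zero or left out. Scoring zero undercounts repeats; leaving out discards observed time and is selective if leaving is linked to poor relief. With no rule, the choice falls to the analyst after the data are in. The VAS and questionnaire outcomes do not have this gap to the same degree, because their mixed model uses partial follow-up.
- **Site.** The randomised temperature is applied on one side at 3-4 branches. If an RFA on the other side or at other levels is counted, events that are not repeats of the index lesion enter both arms and pull the comparison toward no difference. With neither index levels nor the site of later RFAs among the listed items, a same-site repeat could not be rebuilt afterwards from those items.

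At stake is the repeat-RFA part of the secondary hypothesis, not the primary pain-relief result.

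**Working it through.** **Inputs from the documents.** The maximum N is 237 at 1:1, so about 118 per arm. Secondary type I error is 5% with Bonferroni; the number of tests is not stated. No repeat rate, dropout rate or target effect is given for this endpoint, so there is no stated figure to reproduce. N=216 and N=237 were derived for pain relief; 237 is used here only as the group size.

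**Assumptions.** True 12-month same-site risks are 30% at 80°C and 15% at 90°C. There are seven secondary outcomes (VAS, PDI, McGill, Beck, opioids, repeats, complications), so alpha = 0.05/7 = 0.0071 and z = 2.690. At 0.05, z = 1.960.

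**Power formula.** SE = √{[p1(1−p1) + p2(1−p2)]/118}; power = Φ(|p1−p2|/SE − z).

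**Base case.** SE = √[(0.2100 + 0.1275)/118] = 0.0535, and 0.15/0.0535 = 2.805. At 0.05: Φ(0.845) = 0.80. At 0.0071: Φ(0.115) = 0.55. A pooled variance under the null gives 0.79 and 0.53.

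**A. Leavers exit evenly over the year and are scored by what was seen.** With constant hazard h = −ln(1−p), the chance that a leaver's repeat is seen before exit is 1 − p/h: 0.159 for p = 0.30 and 0.077 for p = 0.15. For a leaving fraction d, observed risk = (1−d)p + d(1 − p/h). With 20% leaving in both arms: 0.8×0.30 + 0.2×0.159 = 0.272, and 0.8×0.15 + 0.2×0.077 = 0.135.

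**B. A share of would-be repeaters leaves first and is scored zero.** With 20%: 24% v 12%. With 30%: 21% v 10.5%.

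**C. Unrelated RFAs at rate c in both arms, independent of the index site, all counted.** Observed risk = 1 − (1−p)(1−c).

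| Scenario | 80°C v 90°C | OR | Power at 0.05 | Power at 0.0071 |
|---|---|---|---|---|
| Base | 30.0% v 15.0% | 0.41 | 0.80 | 0.55 |
| A: 20% and 20% leave | 27.2% v 13.5% | 0.42 | 0.75 | 0.48 |
| A: 30% and 10% leave | 25.8% v 14.3% | 0.48 | 0.61 | 0.32 |
| A: 10% and 30% leave | 28.6% v 12.8% | 0.37 | 0.86 | 0.64 |
| B: 20% of repeaters | 24.0% v 12.0% | 0.43 | 0.68 | 0.40 |
| B: 30% of repeaters | 21.0% v 10.5% | 0.44 | 0.61 | 0.33 |
| C: c = 5% | 33.5% v 19.3% | 0.47 | 0.71 | 0.43 |
| C: c = 10% | 37.0% v 23.5% | 0.52 | 0.63 | 0.34 |
| C: c = 20% | 44.0% v 32.0% | 0.60 | 0.48 | 0.22 |

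**No true difference.** Under A with true risks of 30% in both arms, leaving rates of 30% and 10% give 25.8% v 28.6%, OR 1.15. Under B with true risks of 20% in both arms, losing 20% v 5% of repeaters gives 16% v 19%, OR 1.23. That false difference would be declared significant in about 9% of trials at 0.05 and 2% at 0.0071.

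**Dropping instead of scoring zero.** If 20% of would-be repeaters in each arm are dropped, the risks are 0.24/0.94 = 25.5% and 0.12/0.97 = 12.4%. The risk difference falls from 15.0 to 13.2 points, while the OR stays at (0.12/0.85)/(0.24/0.70) = 0.41. If the loss is 20% v 5% with true risks of 20%, dropping gives 0.16/0.96 = 16.7% v 0.19/0.99 = 19.2%, so the false difference remains.

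**The case against.** The strongest reply is that the plan is silent here, not wrong. Three stronger readings are tempting, and the documents support none of them.

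1. **Leavers count as no repeat.** A reader might infer this from the rule that keeps their data. The rule never says that an unseen period is scored zero. An incomplete count could be treated as missing, and data from after withdrawal may be used. Phone and mail follow-up, and the exclusion of people who decline follow-up, should also limit loss.
2. **Unrelated RFAs count as failures of the index lesion.** The fallback sentence "we will use a binary outcome of any RFA procedure comparing two groups of patients" stands under a heading about repeats and collapses a repeat count, so it can be read as any repeat. Repeats after an index procedure may naturally mean that same procedure. The plan does not use the word failure.
3. **Early stopping cuts follow-up short.** Sample size considerations gives a "cumulative 8%, 37%, 75%, and 100% chance of crossing a boundary" under the alternative. That is a chance of crossing. Nothing says that enrolled patients then leave follow-up or that this endpoint is analysed before month 12, and the primary hypothesis itself needs the 12-month visit.

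Two further replies have force. A fixed 12-month binary or ordinal endpoint is legitimate when status is complete. And censoring assumes that leaving is unrelated to the need for a repeat, so Cox or Kaplan-Meier alone does not cure informative dropout.

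What remains is that the chosen model cannot use a partial year, no rule replaces that, and neither the definition nor the listed data items fix the site of a repeat.

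**Conclusion.** The point holds as a limited one on a secondary endpoint. Incomplete years *may* be scored as no repeat or dropped, and RFAs elsewhere *may* be counted; the plan prescribes neither.

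Equal loss unrelated to outcome mainly costs power. Bias arises when loss differs by arm or is related to outcome, and its direction depends on which arm loses more: in the illustration the OR moves from 0.41 to between 0.37 and 0.48. Counting unrelated RFAs at equal rates dilutes the effect, to an OR of 0.47-0.60 for rates of 5-20%.

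Every rate behind these figures is assumed. Power quoted at 0.05 would flatter the endpoint: with seven secondary tests assumed, 30% v 15% has about 55% power, not 80%, before any loss or dilution. The change is worth making because it is cheap and because the site of a repeat has to be settled at data capture.

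**What to change.** - **Outcomes Data and Technique related data:** record the index levels, and the date, side and levels of each later RFA. Define the endpoint as repeat RFA on the index side at one or more index levels within 12 months. List other RFAs separately by arm.
- **Data Analysis, repeat procedures:** analyse time from index RFA to first such repeat, censored at last contact or 12 months, by log-rank test and Cox model. Report the Kaplan-Meier 12-month risk difference, and describe the number of repeats by group.
- **Incomplete follow-up:** for patients with missed visits who have not refused, complete 12-month status from the department's own procedure records. This step is what addresses informative dropout; censoring alone does not.
- **Power:** any figure quoted for this endpoint should state its assumed rates and use the Bonferroni-adjusted secondary alpha.

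The cost is revised wording, the index levels, three fields per later procedure and a record look-up. Second and later repeats are then only described, though the plan already allows that they may be very rare. RFAs done at other institutions may be missed.

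### The primary hypothesis claims no excess harm at 90°C, but the plan offers only a test for a difference, with no between-group interval and no criterion for the claim

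*Combined protocol and SAP*

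**What the plan says.** Under Specific Hypotheses, the primary hypothesis joins a benefit claim to a safety claim: more relief at 90°C "when compared to ablation at 80°C with no additional adverse events". The secondary hypothesis repeats the safety part: "no additional unwanted adverse events and/or complications along with less need to repeat RFA procedure over one year follow-up period".

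The primary outcome under Outcomes Data is efficacy alone: "Overall pain relief (i.e. percent of improvement) at each visit mentioned above". The primary analysis and the sample size also concern pain relief only.

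The Complications paragraph, within the secondary analyses, plans three things:

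- Description by arm: "Incidence of each individual complication will be reported for each group, with confidence intervals".
- A composite: "Possible adverse events (persistent paresthesia, nerve injury, bleeding and infection) will be summarized into a single composite binary outcome, i.e., any versus none".
- A comparison of that composite: "The risk of experiencing one or more adverse events will be compared between RFA at 90°C and RFA at 80°C groups using logistic regression".

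The next paragraph adds: "Type I error will be controlled at 5% for the secondary outcomes using the Bonferroni correction". It does not say how many hypotheses are counted or whether the adverse-event test is one of them. The Sample size section says that safety results go to the Data and Safety Committee, without a safety criterion. The documents give no expected event rate, margin, interval for the between-group difference, or rule for sparse events.

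**The concern.** The safety clause asserts the absence of an excess. A test of the null hypothesis of equal risks can reject equality, but failing to reject it does not show equality or bound the excess. If this test is the only between-group result, a report could state that the hotter lesion brought no extra adverse events while a several-fold increase is still compatible with the data.

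A multiplicity correction pushes the same way. It guards against false claims of benefit across many endpoints. Applied to a harm comparison, it raises the evidence needed before harm is declared and so makes a reassuring result easier to obtain.

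**Working it through.** **Inputs from the documents.** Allocation is 1:1 and the maximum N is 237, so 237/2 = 118.5; I use 118 per arm. No dropout allowance is stated.

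**The plan's own figure.** The only sample size target is for pain relief. From the category table under Sample size considerations, P(90°C better) = 0.648. Noether's formula at two-sided 0.0125 and 90% power gives N = (2.498 + 1.282)² / (12 × 0.25 × 0.148²) ≈ 218 (unrounded P = 0.6477), or 214 with a tie correction. The stated 216 is reproduced. It has no safety input, so it gives no assurance about the safety clause.

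**Assumptions.**

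- Seven secondary tests: VAS, PDI, McGill, Beck, opioid use, repeat procedures, complications. Then 0.05/7 = 0.0071. The count is mine.
- Event risks are illustrative, shown over a range.
- The Complications paragraph does not name the test statistic, so both Wald and likelihood-ratio tests are shown, unadjusted for covariates.

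**A single result.** Take 10/118 at 90°C and 2/118 at 80°C.

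- Risk difference: 8.5% − 1.7% = 6.8 points; Newcombe 95% interval +1.1 to +13.3.
- Log odds ratio: ln[(10 × 116)/(2 × 108)] = 1.681. SE = √(1/10 + 1/2 + 1/108 + 1/116) = 0.786. Wald z = 2.14, P = 0.032.
- Likelihood-ratio P = 0.013; Fisher P = 0.034.

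All three P values are below 0.05 and above 0.0071. With 2 events at 80°C, the Wald test needs 15 at 90°C to reach 0.0071.

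For 6 versus 2, Fisher P = 0.28 and the interval is −1.7 to +9.1 points. That result is non-significant at either level, yet an excess of 9 points is not excluded.

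**Power.** Sum the binomial probabilities of all tables (x, y), 118 per arm, in which the test rejects:

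| Assumed risk, 80°C vs 90°C | 0.0071: Wald / LR | 0.05: Wald / LR |
|---|---|---|
| 2% vs 6% | 0.3% / 14% | 19% / 40% |
| 2% vs 8% | 3% / 31% | 43% / 63% |
| 5% vs 10% | 4% / 11% | 28% / 32% |
| 5% vs 15% | 36% / 49% | 73% / 76% |

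**Zero cells.** P(no events in at least one arm) = 1 − [1 − (1 − p₁)¹¹⁸][1 − (1 − p₂)¹¹⁸].

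- 1% vs 1%: 0.99¹¹⁸ = 0.305, so 1 − 0.695² = 52%.
- 2% vs 6%: 9%.
- 5% vs 10%: 0.2%.

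A zero cell leaves the ordinary log odds ratio without a finite estimate. Stopping at the second look leaves about 59 per arm, and the 1% vs 1% figure becomes 80%. The plan gives a cumulative 37% chance of crossing a boundary by then under its alternative.

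**The case against.** Several stronger readings are tempting, and the documents do not support them.

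- **That the test has almost no power.** This depends on rates the documents do not give and on a Wald test that the Complications paragraph does not name; Wald is named for the mixed models and for opioid use. At 5% versus 15%, power is 36% to 49% even at 0.0071, and 73% to 76% at 0.05.
- **That the model often cannot be fitted.** Zero cells are common only near a 1% risk or after an early stop. The endpoint is a four-part composite, and nothing in the documents puts its risk that low. A likelihood-ratio test from the same model also copes with a zero cell in one arm.
- **That Bonferroni certainly applies.** Outcomes Data lists adverse events under their own heading, apart from the secondary outcomes. The other reading rests on the secondary hypothesis and on where the Complications paragraph sits. It is the more natural reading, but it is not explicit.
- **That the investigators intend to read non-significance as proof of safety.** No sentence says so. It is a risk left open, not a stated rule.

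It is also fair to say that the logistic test is not the whole safety plan, since per-arm intervals and committee review are included. But intervals for each complication in each arm do not bound the difference in the composite, and the committee is given no criterion. These points limit how strongly the concern can be put. They do not supply what the safety clause needs.

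**Conclusion.** The concern holds in this form: one part of the primary hypothesis has no analysis that could support it. That conclusion needs no assumption about event rates, test statistic or alpha.

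The size of the problem does depend on assumptions. If the correction applies with seven tests, power to declare a doubling from 5% to 10% is 4% to 11%, and a fivefold observed excess (10 versus 2) would be non-significant. If adverse events lie outside the family, power for that doubling rises to 28% to 32% and 10 versus 2 becomes significant at 0.05, but a non-significant result still would not establish the clause. Estimation failure from zero cells is a secondary matter, worth guarding against because the event rate is unknown. Efficacy conclusions are unaffected.

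**What to change.** In the Complications paragraph and the multiplicity sentence:

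1. State that the composite adverse-event comparison is outside the secondary Bonferroni family.
2. Report the risk difference, 90°C minus 80°C, with an uncorrected two-sided 95% score-type interval (Newcombe, for example). For any test, name a method that tolerates zero cells: exact, likelihood-ratio or Firth would each serve.
3. State that non-significance will not be interpreted as showing the safety clause.
4. Either give the upper confidence limit as the safety conclusion, or remove the clause from the primary hypothesis.

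The cost is wording only: no patients or data are added. The safety conclusion becomes an upper limit instead of a statement of no difference, and the uncorrected comparison carries a slightly higher chance of a false safety signal.
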